13.1.1 SENSITIVITY ANALYSES

The following sensitivity analyses will be conducted.

13.1.1.1 SENSITIVITY ANALYSIS I

The hypothetical strategy will be used for the intercurrent event. All missing data will be imputed assuming missing not at random (imputing from the vehicle treatment arm). The following SAS code will be used to generate the multiple imputation datasets:

```
PROC MI DATA=INDATA SEED=43623 NIMPUTE=20 OUT=MADATA MINIMUM=0 MAXIMUM=4  
ROUND=1;  
    BY TRT;  
    MCMC IMPUTE=MONOTONE;  
    VAR BASE DAY08 DAY15 DAY22 DAY43;  
RUN;  
PROC MI DATA=MADATA SEED=346238 NIMPUTE=1 OUT=OUT1 MINIMUM = . 0 0 0 0 0 MAXIMUM  
= . 4 4 4 4 4 ROUND = . 1 1 1 1 1;  
    BY _IMPUTATION_;  
    CLASS TRT;  
    MONOTONE REG(DAY08 = BASE/DETAILS);  
    MONOTONE REG(DAY15 = BASE DAY08/DETAILS);  
    MONOTONE REG(DAY22 = BASE DAY08 DAY15/DETAILS);  
    MONOTONE REG(DAY43 = BASE DAY08 DAY15 DAY22/DETAILS);  
    MNAR MODEL(BASE DAY08 DAY15 DAY22 DAY43 / MODELOBS=(TRT='Vehicle'));  
    VAR BASE DAY08 DAY15 DAY22 DAY43;  
RUN;
```

13.1.1.2 SENSITIVITY ANALYSIS II

The hypothetical strategy will be used for the intercurrent event. All missing data will be imputed assuming missing at random (imputing from the same treatment arm as the subject with missing data) using similar code as provided in Section 13.1 for the primary efficacy analysis.

13.1.1.3 SENSITIVITY ANALYSIS III

The primary efficacy analysis will be performed using the PP set with observed data only. Treatment comparisons will also be made using the difference of proportion test and Pearson's chi-squared test or Fisher's exact test if any of the expected cell counts are less than five as an additional sensitivity analysis.

13.1.1.4 SENSITIVITY ANALYSIS IV

The primary efficacy analysis will be performed using the FAS set with observed data only. Treatment comparisons will also be made using the difference of proportion test and Pearson's chi-squared test or Fisher's exact test if any of the expected cell counts are less than five as an additional sensitivity analysis.

13.1.1.5 SENSITIVITY ANALYSIS V

The hypothetical strategy will be used for the intercurrent event. All missing data will be imputed as failure. Treatment comparisons will also be made using the difference of proportion test and Pearson's chi-squared test or Fisher's exact test if any of the expected cell counts are less than five as an additional sensitivity analysis.

13.2 Secondary Analyses

The secondary efficacy endpoints proportion of subjects with *Demodex* eradication at Day 43 and proportion of subjects composite cure based on collarette and erythema scores at Day 43 and will be conducted on the FAS.

As specified in Section 8.2, missing data without withdrawal or withdrawal due to reasons other than lack of efficacy or AEs will be imputed employing MI using randomized treatment-based MCMC methodology. The following SAS code will be used to generate the multiple imputation datasets:

```
PROC MI DATA=INDATA SEED=56636 NIMPUTE=20 OUT=OUT1 MINIMUM=0 MAXIMUM=4 ROUND=1;
  BY TRT;
  MCMC INITIAL=EM;
  VAR BASE DAY08 DAY15 DAY22 DAY43;
RUN;
```

The multiple imputation datasets will be used to calculate cure based on each respective secondary endpoint. The following SAS code will then be used to calculate the difference of proportions for each imputed dataset and combine the analyses across imputations:

```
PROC SORT DATA=OUT1; BY _IMPUTATION_; RUN;
PROC FREQ DATA=OUT1;
  BY _IMPUTATION_ ;
  TABLES TRT*CURE / RISKDIFF CL;
  ODS OUTPUT RISKDIFFCOL2=PROP;
RUN;
PROC MIANALYZE DATA=PROP;
  WHERE ROW='Difference';
  MODELEFFECTS RISK;
  STDERR ASE;
  ODS OUTPUT PARAMETERESTIMATES=PEST;
RUN;
```

Comparisons will be one-sided using an α of 0.025.

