3.2 Schedule of Visits and Assessments

The schedule of visits and assessments is provided in Table 2.

Table 2. Schedule of Visits and Assessments

Procedures	Screening Day -14 to 1	Enrollment/Initiation of Study Treatment Day 1	Day 8 ± 3 days	Day 15 ± 3 days	Day 22 -3/+4 days	Day 43 -3/+7 days	Day 57 -6/+14 days
Informed consent	X						
Demographics	X						
Medical/ophthalmic history	X						
Concomitant medication review	X	X	X	X	X	X	X
Corrected distance visual acuity (CDVA)	X	X ^a	X	X	X	X	X
Slit lamp biomicroscopy	X	X ^a	X	X	X	X	X
Collarette grading; erythema	X		X	X	X	X	X
Corneal staining		X	X	X	X	X	X
Intraocular pressure		X				X	X
Demodex count	X			X	X	X	X
Dilated fundus examination		X				X	
Urine pregnancy test ^b	X					X	
Randomization		X					
Dispense study drug; diary		X					
Collection and review of participant diary			X	X	X		
Collection of study drug and return to participant			X	X	X		
Adverse event review and evaluation		X	X	X	X	X	X
Collect study drug; diary						X	
Study exit						X ^c	X ^d

a: If the Screening and Day 1 visits are completed on the same day, this test does not have to be repeated.

b: Women of childbearing potential

c: For Cohort 1 participants

d: For Cohort 2 participants

4. Study Treatments

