12.1 Dosing Compliance

Dosing compliance (% compliance) will be assessed by calculating the number of actual doses received and comparing that to the number of expected doses as follows:

$$\text{Compliance (\%)} = \frac{\text{Number of Actual Doses Received} \times 100\%}{\text{Number of Expected Doses}}$$

The number of actual doses received will be recorded in the CRF (first dose in Study Drug Instillation CRF and remaining doses in Study Drug Diary CRF). Two doses are expected each day except only one dose should be completed on the last day of the study. The number of expected doses that will be used for calculating compliance will be calculated as:

$$2 \times (\text{Date of Last Dose} - \text{Date of First Dose}) + 1$$

for all subjects, regardless of study completion status.

A categorical dosing compliance variable will also be derived as non-compliant (<80%), compliant ($\geq 80\%$ and $\leq 125\%$), and over compliant ($>125\%$).

Dosing compliance (%) will be summarized with continuous descriptive statistics for each treatment group, as well as by site, sex, age, and race using the safety set. The compliance category defined above will be summarized with discrete summary statistics.

A subject listing of dosing compliance will also be produced.

13. Efficacy Analyses

The efficacy assessments performed include the following:

- Assessment of collarette grade
- Assessment of erythema grade
- Eyelash epilation and mite counts

Collarette grade is determined based on number of lashes with collarettes per eyelid (Table 3). The proportion of subjects cured in the upper eyelid of the analysis eye based on collarette grade will be summarized by visit and treatment group. The percentage of subjects at each grade will be summarized by visit and treatment group, as well as by site, sex, age, and race. The proportion of subjects cured in the upper eyelid of the analysis eye by visit and treatment group will be displayed graphically by bar charts.

Table 3. Collarette Grading

Grade	Clinical Interpretation
0	0 to 2 lashes have collarettes per eyelid
1	3 to 10 lashes have collarettes per eyelid
2	More than 10 but less than $\frac{1}{3}$ of lashes have collarettes per eyelid
3	$\frac{1}{3}$ or more but less than $\frac{2}{3}$ of lashes have collarettes per eyelid
4	$\frac{2}{3}$ or more of lashes have collarettes per eyelid
0.5 unit increments ARE NOT allowed	

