13.1 Primary Analysis

The primary efficacy endpoint is cure based on collarette score of 0 for the upper eyelid of the analysis eye at Day 43. The primary efficacy endpoint will be conducted on the FAS, with intercurrent events handled as described in Section 8.2. Descriptive statistics will be presented by treatment arm. Testing of the percentage of subjects cured at Day 43 based on the collarette grade will be completed using a difference of proportions test.

As specified in Section 8.2, missing data without withdrawal or withdrawal due to reasons other than lack of efficacy or AEs will be imputed employing MI using randomized treatment-based MCMC methodology.

The following SAS code will be used to generate the multiple imputation datasets:

```
PROC MI DATA=INDATA SEED=56636 NIMPUTE=20 OUT=OUT1 MINIMUM=0 MAXIMUM=4 ROUND=1;
  BY TRT;
  MCMC INITIAL=EM;
  VAR BASE DAY08 DAY15 DAY22 DAY43;
RUN;
```

The multiple imputation datasets will be used to calculate cure based on a collarette score of 0 at Day 43. The following SAS code will then be used to calculate the difference of proportions for each imputed dataset and combine the analyses across imputations:

```
PROC SORT DATA=OUT1; BY _IMPUTATION_; RUN;
PROC FREQ DATA=OUT1;
  BY _IMPUTATION_ ;
  TABLES TRT*CURE / RISKDIFF CL;
  ODS OUTPUT RISKDIFFCOL2=PROP;
RUN;
PROC MIANALYZE DATA=PROP;
  WHERE ROW='Difference';
  MODELEFFECTS RISK;
  STDERR ASE;
  ODS OUTPUT PARAMETERESTIMATES=PEST;
RUN;
```

Statistical comparison between treatment groups will be one-sided using an α of 0.025.

In addition to the primary analysis, supplementary analyses are proposed under different assumptions for the estimand to assess efficacy in patients who have missing data.

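### SAP 13.2 reuses the collarette imputation step for both secondary endpoints, and it fits neither mite eradication nor the two-score composite

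*SAP*

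**What the plan says.** Section 13.2 sends data missing without withdrawal, or after withdrawal for reasons other than lack of efficacy or adverse events, to multiple imputation within treatment arm. The call is "PROC MI DATA=INDATA SEED=56636 NIMPUTE=20 OUT=OUT1 MINIMUM=0 MAXIMUM=4 ROUND=1", with the variable list "VAR BASE DAY08 DAY15 DAY22 DAY43". It is presented as the code to be run, and its output serves both endpoints: "The multiple imputation datasets will be used to calculate cure based on each respective secondary endpoint".

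Section 13.1 prints the identical step, including the seed, for the primary endpoint, where it belongs: "The multiple imputation datasets will be used to calculate cure based on a collarette score of 0 at Day 43".

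Section 2.2 defines the two secondary endpoints as a mite density of 0, and as collarette and erythema scores both 0, at Day 43. Section 8.5 tests them by Hochberg at one-sided 0.025 once the primary succeeds. Sections 13.2.1 and 13.2.2 add no imputation code. Each adds a sensitivity analysis that counts all missing data as failure.

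**The concern.** The variable list, limits and rounding all describe the collarette grade. Used for mite density or for the composite, they either lack data or sit on the wrong scale. Whoever programs these analyses would have to choose a different model. For two hypotheses that support superiority claims, that choice should be written down before treatment codes are opened. At stake are the prespecified estimates and confidence intervals for eradication and composite cure.

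**Working it through.** **1. Code against schedule and scales.**

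| Feature of the step | Collarette (13.1) | Mite density | Composite |
|---|---|---|---|
| DAY08 in the model | graded at Day 8 | "Demodex count" scheduled at Screening, Days 15, 22, 43 and 57 only (Table 2) | both scores graded at Day 8 |
| Limits 0 to 4 | Table 3 grades | no visible basis | erythema runs 0 to 3 (Table 4) |
| ROUND=1 | whole grades only | depends on the unit | whole grades only |
| One series | sufficient | sufficient | two scores needed |

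The visible Day 8 list in protocol 1.2 also shows no mite count, so no observed value can inform DAY08 for eradication. The upper limit comes from the collarette scale: "Collarette grade is determined based on number of lashes with collarettes per eyelid (Table 3"), with top grade 4. The density unit is not visible; SAP Section 13 says only "Eyelash epilation and mite counts". If density can be fractional, rounding turns imputed values below 0.5 into eradication. If it is a whole-number count, the misfit is DAY08 and MAXIMUM=4.

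**2. The plan's own figure.** Section 5 gives 99% power for each secondary endpoint with 150 per arm at one-sided 0.025. With p̄ the mean of the two rates,

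z = [(p1 − p2) − 1.96 √(2p̄(1 − p̄)/150)] / √{[p1(1 − p1) + p2(1 − p2)]/150}.

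- Eradication (73.3% vs 21.1%): (0.522 − 0.113)/0.0491 = 8.3.
- Composite (73.3% vs 10.5%): z = 11.7.

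Both give power above 99.9%, so the stated figure is reproduced.

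**3. Share imputed.** Of 209 per arm (Section 5), 5%, 10% and 30% are 10, 21 and 63 subjects. The 5% and 10% are assumptions. The 30% is the SAP's discontinuation contingency and so an upper limit, because withdrawals for lack of efficacy or adverse events bypass MI. A 10-point error in one arm's imputed rate moves the difference by share × 10 = 0.5, 1.0 or 3.0 points.

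**4. Composite judged on the collarette series alone.** Cure among imputed subjects is overstated by 80.0 − 73.3 = 6.7 points (TP-03) and 15.8 − 10.5 = 5.3 points (vehicle).

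| Share | TP-03 | Vehicle | Difference |
|---|---|---|---|
| 5% | +0.3 | +0.3 | +0.1 |
| 10% | +0.7 | +0.5 | +0.1 |
| 30% | +2.0 | +1.6 | +0.4 |

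**5. Composite with the two scores imputed as if independent.** Given the planning rates, the erythema cure rate e must lie between the composite rate and 100 − collarette rate + composite rate: 73.3% to 93.3% for TP-03 and 10.5% to 94.7% for vehicle. Imputed composite cure is the collarette rate × e:

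- TP-03: 0.80 × 0.733 = 58.6% to 0.80 × 0.933 = 74.6%, against 73.3%.
- Vehicle: 0.158 × 0.105 = 1.7% to 0.158 × 0.947 = 15.0%, against 10.5%.

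Full independence is an extreme, since observed earlier visits carry some of the correlation.

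**6. Worst case for the test.** Let every imputed TP-03 subject fail and every imputed vehicle subject succeed. With share s, TP-03 is p(1 − s) and vehicle is p(1 − s) + s; z uses the unpooled standard error with 209 per arm.

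| Share | Eradication | z | Composite | z |
|---|---|---|---|---|
| 5% | 69.6% vs 25.0% | 10.2 | 69.6% vs 15.0% | 13.6 |
| 10% | 66.0% vs 29.0% | 8.1 | 66.0% vs 19.4% | 10.9 |
| 30% | 51.3% vs 44.8% | 1.3 | 51.3% vs 37.4% | 2.9 |

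**7. Missing as failure at 30%.** Eradication is 0.7 × 73.3 = 51.3% vs 0.7 × 21.1 = 14.8%, a difference of 36.5 points. The composite is 51.3% vs 7.4%, a difference of 44.0 points. Power exceeds 99.9% even at one-sided 0.0125.

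**8. Eradication, illustration only.** The densities below are assumed, with data missing completely at random and a within-arm normal regression of Day 43 on baseline, Day 15 and Day 22. Shifts are in the treatment difference, in points.

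| Assumed density | 5% imputed | 10% | 30% |
|---|---|---|---|
| Whole-number counts (non-zero means 1.3–4 TP-03, 2–8 vehicle), MAXIMUM=4 alone | 0 to −0.6 | 0 to −1.2 | 0 to −3.5 |
| Fractional (non-zero means 0.3–1.5 and 0.5–2.5), limits plus rounding | −1.9 to +1.8 | −3.7 to +3.7 | −11.2 to +11.1 |

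A cruder model, drawing from each arm's marginal normal with non-zero means of 0.3 to 3.0, gives a difference of about 39 to 46 points against 52.2 at 30% imputed. The direction and size of the error therefore depend on densities the documents do not give.

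**The case against.** The best defence is that the code is a template. Its dataset and variable names are generic, and the reference to each respective endpoint suggests one run per measure, with the collarette and erythema outputs merged by subject and imputation number. This stands only in part. Section 13.2 does not say so, whereas Sensitivity Analysis II does call its code similar to that of 13.1. A rerun per measure still leaves DAY08 empty for mites and MAXIMUM=4 unsupported for density. Separate runs also do not model the relation between the two scores.

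Four further points stand and limit the finding:

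- Much of both documents is redacted, so the density limits have no visible basis rather than demonstrably none.
- The impossible erythema grade 4 is nearly immaterial, since 3 and 4 are both non-cure. Under assumed means of 0.3 to 2.0 and SDs of 0.5 to 1.0, it lowers the imputed grade-0 rate by at most 0.8 points, or 0.8 × 0.30 = 0.24 points in an arm with 30% imputed.
- The simulated eradication ranges reflect the assumptions chosen and should not set the severity.
- The missing-as-failure analyses do not use this code. They are a real backstop for the significance conclusion, though as sensitivity analyses they do not supply the prespecified main estimate or interval.

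**Conclusion.** The concern holds. As printed, the imputation step for the two Hochberg-tested secondary endpoints has a variable with no data and limits from another scale for eradication, and too few variables for the composite. This follows from comparing the code with Table 2, Tables 3 and 4 and Section 2.2; no simulation is needed.

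The effect on significance is small. At the planning rates and 209 per arm, no imputation error can reverse either test with up to 10% imputed. At 30%, only the extreme worst case takes eradication below the critical value (z 1.3), while the composite stays above it (z 2.9). The bias in the estimates cannot be fixed from the documents, because the density distribution and the share imputed are unknown. This should be corrected before unmasking, but it does not threaten the trial's main conclusion.

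**What to change.** Put endpoint-specific imputation code in Section 13.2 before unmasking.

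- **Eradication.** Drop DAY08, MAXIMUM=4 and ROUND=1. Impute Day 43 eradication as 0/1 within treatment, for example by logistic regression on baseline, Day 15 and Day 22 density, with missing Day 15 or Day 22 values imputed in the same step. Removing the limits alone is not enough, because an unrounded normal draw practically never equals 0. In simulations under assumed densities (209 per arm, 10% or 30% missing), the logistic version was within −1.7 to +2.1 points among imputed subjects (simulation error up to 0.9), with no convergence failure in 9,600 fits.
- **Composite.** Impute collarette and erythema together within treatment, using baseline and Days 8, 15, 22 and 43, and then derive cure as both equal to 0. The existing MCMC step is sufficient with both series in one variable list and limits of 0–4 and 0–3. Sensitivity Analysis I already lists limits by variable ("4 4 4 4 4 ROUND = . 1 1 1 1 1"). An ordered-grade model would avoid rounding but is optional; if chosen, name the MCMC version as the fallback for non-convergence.
- **Text.** State in 13.2 any departure from the MCMC method of 8.2, and leave 8.2 and the primary analysis unchanged. Correct the test sentence in 13.2.2, which names mite eradication instead of composite cure.

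The cost is SAP text and some programming, with no new data. The imputation method would differ between the primary and secondary endpoints. An ordered-grade model would be thin within arm: with 10% missing, about 209 × 0.9 × 0.158 = 30 vehicle subjects at collarette 0 and 209 × 0.9 × 0.20 = 38 TP-03 subjects above 0 (23 and 29 with 30% missing).

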13.2.1 FIRST SECONDARY EFFICACY ENDPOINT

The first secondary efficacy endpoint is cure based on proportion of subjects with *Demodex* eradication of the analysis eye at Day 43, with intercurrent events handled as described in Section 8.2. Descriptive statistics will be presented by treatment arm. Testing of the percentage of subjects cured at Day 43 based on the *Demodex* eradication will be completed using a difference of proportions test. In addition, a sensitivity analysis will be conducted in which all missing data will be imputed as failure. The difference of proportion test and Pearson's chi-squared (or Fisher's exact test if any of the expected cell counts are less than five) will be used in this sensitivity analysis.

13.2.2 SECOND SECONDARY EFFICACY ENDPOINT

The second secondary efficacy endpoint is cure based on proportion of subjects composite cure based on collarette and erythema scores of the analysis eye at Day 43, with intercurrent events handled as described in Section 8.2. Descriptive statistics will be presented by treatment arm. Testing of the percentage of

subjects cured at Day 43 based on the *Demodex* eradication will be completed using a difference of proportions test. In addition, a sensitivity analysis will be conducted in which all missing data will be imputed as failure. The difference of proportion test and Pearson's chi-squared (or Fisher's exact test if any of the expected cell counts are less than five) will be used in this sensitivity analysis.

Term	Percentage
GMOs	95
Organic	90
Natural	85
Artificial	75
Organic	90
Natural	85
Artificial	75
Organic	95
Natural	90
Artificial	85

14. Safety Analyses

All safety analyses will be conducted using the safety set.

14.1 Treatment Exposure

Extent of treatment exposure for completed or discontinued subjects will be calculated in days using the following:

Extent of Exposure (days) = (Date of Last Dose – Date of First Dose) + 1

Extent of treatment exposure for subjects who were lost to follow-up will be calculated in days using the following:

$$\text{Extent of Exposure (days)} = (\text{Date of Last Recorded Visit} - \text{Date of First Dose}) + 1$$

Extent of treatment exposure for each subject exposed to study drug will be summarized with continuous descriptive statistics for each treatment group using the safety set. A subject listing of treatment exposure will also be produced.

14.2 Adverse Events

An Adverse Event (AE) is defined as any untoward medical occurrence associated with the use of a drug in humans, whether or not the event is considered drug-related. All AEs will be coded using the MedDRA version 23.0.

Treatment-emergent adverse events (TEAE) are defined as any event that occurs or worsens on or after the day that randomized study treatment is initiated. It is not anticipated that any AEs will occur before treatment. However if in the unlikely event an AE recorded in the eCRF which began prior to treatment will not be included in the summary tables but will be included in the AE data listings.

Severity of an AE is defined as a qualitative assessment of the degree of intensity of an AE as determined by the Investigator or reported to him/her by the subject. The assessment of severity is made irrespective of relationship to study drug or seriousness of the event and should be evaluated according to the following scale:

- **Mild** - Events require minimal or no treatment and do not interfere with the subject's daily activities.
- **Moderate** - Events result in a low level of inconvenience or concern with the therapeutic measures. Moderate events may cause some interference with functioning.
- **Severe** - Events interrupt a subject's usual daily activity and may require systemic drug therapy or other treatment. Severe events are usually potentially life-threatening or incapacitating.

The relationship of each AE to the study drug should be determined by the Investigator using these explanations:

- **Definitely Related** – Evidence indicates a reasonable temporal sequence of the event with the study drug administration exists or that the association of the event with study drug administration is unknown and the event is not reasonably supported by other conditions such that:
 - There is a clinically plausible time sequence between onset of the AE and study treatment administration; and/or
 - There is a biologically plausible mechanism for study treatment causing or contributing to the AE; and
 - The AE cannot be reasonably attributed to concurrent/underlying illness, other drugs or procedures.

- **Potentially Related** – Evidence indicates a possible relationship to the study drug such that:
 - The event occurs within a reasonable period of time relative to the treatment that makes a causal relationship possible, but plausible explanations may also be provided by other causes such as other drugs, products, chemicals, underlying disease, environment, etc.
 - The event is possibly related to the study treatment.
- **Not Related** – Evidence indicates no plausible direct relationship to the study drug such that:
 - A clinically plausible temporal sequence is inconsistent with the onset of the AE and drug administration; and/or
 - A causal relationship is considered biologically implausible.
 - The AE can be attributed to concurrent/underlying illness, other drugs, or procedures.

Definitely and potentially related TEAEs are considered treatment-related TEAEs.

An AE or suspected adverse reaction is considered "serious" if, in the view of either the investigator or sponsor, it results in any of the following outcomes: death, a life-threatening AE, inpatient hospitalization or prolongation of existing hospitalization, a persistent or significant incapacity or substantial disruption of the ability to conduct normal life functions, or a congenital anomaly/birth defect. Important medical events that may not result in death, be life-threatening, or require hospitalization may be considered serious when, based upon appropriate medical judgment, they may jeopardize the participant and may require medical or surgical intervention to prevent one of the outcomes listed in this definition. Serious adverse events include drug deficiencies that might have led to a SAE if a) suitable action had not been taken or b) intervention had not been made or c) if circumstances had been less fortunate.

A planned hospitalization for a pre-existing condition without a serious deterioration in health is not considered to be a SAE. Hospitalization for less than 24 hours is not considered a SAE unless the precipitating event was unanticipated and also related to the investigational drug.

Events that are considered sight-threatening in the opinion of the investigator will be considered SAEs.

An overall summary will be presented that includes the number of events and the number and percentage of subjects who experienced at least one TEAE, by treatment group and over all subjects. This summary will also include breakdowns of TEAEs further categorized as ocular or non-ocular, treatment-related TEAEs, serious adverse events (SAE), TEAEs leading to death, and TEAEs by maximum severity.

Ocular and non-ocular TEAEs will be summarized using discrete summary statistics and presented by treatment group at the subject and event level by SOC and PT. If a subject reports the same PT multiple times, that PT will only be counted once within that SOC. As with the PT, if a subject reports multiple conditions within the same SOC, that SOC will only be counted once. In the summary, SOCs will be summarized in ascending alphabetical order; PTs will be listed in order of descending frequency for all subjects within each SOC.

Separate summaries will be provided for the following categories of AEs:

- Ocular TEAEs
- Non-ocular TEAEs
- Ocular TEAEs by SOC, PT, and Severity
- Non-ocular TEAEs by SOC, PT, and Severity
- Ocular TEAEs by SOC, PT, and Strongest Relationship to Study Drug
- Non-ocular TEAEs by SOC, PT, and Strongest Relationship to Study Drug
- Ocular TEAEs by SOC, PT, Severity, and Strongest Relationship to Study Drug
- Non-ocular TEAEs by SOC, PT, Severity, and Strongest Relationship to Study Drug
- TEAEs That Led to Premature Discontinuation
- Treatment-emergent SAEs

Summaries of TEAEs by maximum severity will be presented for ocular AEs and non-ocular AEs separately. The number of subjects with any TEAEs (along with percentages) will be tabulated by SOC and PT within each SOC by treatment group. To count the number of subjects with any TEAEs, if a subject has multiple TEAEs coded to the same PT, the subject will be counted once under the maximum severity.

All AEs and TEAEs will be presented in a subject listing. The TEAEs leading to study treatment discontinuation and resulting in temporary discontinuation of study drug will be listed separately. In addition, all SAEs will be presented in a separate listing.

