3.1 General Study Design

[figure not shown]
This is a randomized, controlled, multicenter, double-masked, parallel, phase 2b/3 trial to evaluate the safety and efficacy of TP-03, 0.25%, for the treatment of *Demodex* blepharitis.

A subject's participation is to start with screening at Day -14 to 1. At the Screening visit, potential subjects will be evaluated for eligibility. Prior to performing any study specific procedures, potential subjects must provide informed consent using the current Institutional Review Board (IRB) approved informed consent form. Potential subjects who meet all eligibility criteria can proceed directly to the Day 1 procedures or the Day 1 visit can be scheduled within the next 14 days. If a subject does not come in for the Day 1 visit within 14 days, the Screening visit procedures must be repeated. If the subject is considered eligible for the study at the end of the Screening visit, the subject will be randomized at Day 1 to receive one of the following treatments administered bilaterally two times a day (BID) for approximately 43 days: TP-03, 0.25%, or the TP-03 vehicle. Subjects enrolled in Cohort 2 will also attend Day 57 follow-up. All other subjects are defined as Cohort 1, with final study visit at Day 43.

Study day will be referred to in all tables and listings. Table 1 shows the scheduled study day and the acceptable day window for each study visit:

Table 1. Study Visit Windows

Planned Study Day	Day Window
Day -14 to Day 1 (Screening)	N/A
Day 1 (Randomization)	N/A
Day 8	\pm 3 Days
Day 15	\pm 3 Days

Planned Study Day	Day Window
Day 22	-3/+4 Days
Day 43	-3/+7 Days
Day 57 (Cohort 2 participants only)	-6/+14 Days

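### SAP 14.2 counts worsening events as treatment-emergent, then keeps every AE with a pre-treatment onset out of the summary tables, with no exception for worsening

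*SAP*

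**What the plan says.** SAP 14.2 sets two rules in one paragraph.

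- Definition: a TEAE is "any event that occurs or worsens on or after the day that randomized study treatment is initiated". It covers new events and worsening events, and its boundary is a calendar day.
- Exclusion: after the remark "It is not anticipated that any AEs will occur before treatment", the SAP adds that "an AE recorded in the eCRF which began prior to treatment will not be included in the summary tables". Such AEs are kept for the listings. The test here is onset alone.

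The same section then builds the AE tables on TEAEs. The overall summary gives the number of events and "the number and percentage of subjects who experienced at least one TEAE". The tables by organ class, term, severity, relationship and premature discontinuation, and the table of treatment-emergent SAEs, are also restricted to TEAEs. The listings are wider: "All AEs and TEAEs will be presented in a subject listing", and "all SAEs will be presented in a separate listing".

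SAP 3.1 allows time for an AE to begin before treatment, since Day 1 may follow Screening by up to 14 days.

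**The concern.** A worsening clause exists to capture events that were present before the first dose and became worse on study drug. An onset-only exclusion takes those same events out of the tables. If the programmer follows the exclusion sentence, the words about worsening have no effect for any AE recorded with a pre-treatment start date.

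SAP 2.1 makes assessment of treatment-related adverse effects the primary safety endpoint, and 14.2 identifies the treatment-related events as the TEAEs rated definitely or potentially related. What qualifies as a TEAE, and whether every TEAE is tabulated, therefore decides what the primary safety tables contain. A listing retains the individual event but gives no comparison between arms.

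**Working it through.** No figure in the plan needs reproducing. The check is a comparison of the two rules, followed by one bound.

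**Step 1. Apply both rules to each kind of AE**, with the boundary set by day, as in the definition.

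| AE | Definition | Exclusion sentence | Agree? |
|---|---|---|---|
| Began before the day of first dose, did not worsen | Not a TEAE | Out of tables | Yes |
| Began before the day of first dose, worsened on or after it | TEAE | Out of tables | **No** |
| Began on the day of first dose | TEAE | Not excluded, if *prior* is read by day | Yes |
| Began after the day of first dose | TEAE | Not excluded | Yes |

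Only the second row conflicts. Section 14.2 gives no order of precedence.

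**Step 2. Trace what happens to an event in the second row** if the exclusion sentence is followed.

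- AE summary tables (14.2): omitted.
- AE listing (14.2): kept. SAE listing (14.2): kept if serious.
- Visual acuity, slit lamp, fundus, intraocular pressure and corneal staining summaries (14.3 to 14.5, 14.7, 14.12): unaffected, since none depends on AE onset.

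**Step 3. Bound the effect.**

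- Input: 209 subjects per arm planned for randomization (SAP section 5).
- One subject as a share of an arm: 1/209 = 0.00478, or 0.48 percentage points.
- The overall percentage counts subjects with at least one TEAE. Omitting an event therefore moves it by 0.48 points if the subject has no other TEAE, and by 0 otherwise, so 0.48 is a ceiling per affected subject.
- The same logic applies to a preferred-term row: the subject drops out of it only if no other tabulated event has that term. The event count falls by one for each omitted event.
- The denominator will be the safety set (14, 7.4). If fewer than 209 per arm are dosed, the ceiling rises in proportion.

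**Step 4. Consider how many events there could be.** The documents give no rate. Three features point to a small number: the SAP expects no AEs before treatment, the interval from Screening to Day 1 is at most 14 days (3.1), and Table 2 schedules AE review from Day 1 and not at Screening. No total effect can be calculated.

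**The case against.** The strongest defence is that the definition governs. The AE tables in 14.2 are specified in terms of TEAEs, a worsened event is a TEAE, and so it belongs in them. The exclusion sentence is grammatically broken and follows directly on the remark that no pre-treatment AEs are expected, so it may have been meant only for AEs that are not treatment-emergent. That reading is reasonable, and it means removal is not certain. It does not settle the matter, because the sentence as written turns on onset, has no exception, and is the more specific instruction about the tables.

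A second defence is that conditions present at entry are collected as medical and ophthalmic history at Screening (Table 2; 11.1), while the exclusion speaks only of AEs. If an aggravation is entered as a new AE with an on-treatment start date, it is counted under both rules. This narrows the reach. The readable text does not say how worsening is recorded, so it cannot be relied on to remove the conflict.

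A reader might infer that a worsened event vanishes from all safety reporting. The documents do not support that: the listings keep it, and the examination summaries do not depend on AE dates. Those summaries are only a partial backstop. Slit-lamp and fundus findings are graded in three categories, so worsening within a category shows no shift, and a worsened symptom or non-ocular event need not appear in them at all.

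Finally, SAP 3.5 states only efficacy hypotheses, and the AE summaries are descriptive. No confirmatory safety test is at risk.

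**Conclusion.** The conflict is real and confined to one case: an AE that begins before treatment and worsens on or after the day treatment starts. The definition makes it a TEAE and the exclusion sentence, taken literally, keeps it out of the AE summary tables. The size is probably small: at most 0.48 points on an arm's overall TEAE percentage per affected subject, at 209 per arm, and nothing if the subject has another TEAE. This assumes that worsening is recorded on the original AE with its original start date, and that the exclusion sentence is the one followed.

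Two stronger readings go too far.

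- **Bias in favour of TP-03.** A reader might infer that the rule flatters the active arm. It applies equally to both arms, and the documents give no rate of pre-treatment AEs or of worsening in either. A difference would arise only if worsening were more common on one arm, which nothing in the documents shows.
- **A second conflict on Day 1.** A reader might see one for an event that starts on Day 1 before the first drop. It arises only if *prior to treatment* is read by clock time. The definition works by day, and the date rules in SAP 8.2 do too: some partial start dates are set to the day of first dose, and imputed dates feed treatment-emergence status. Read consistently by day, a Day 1 event is a TEAE. The wording should say so, but the by-day rule is the inclusive one and need not be narrowed.

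**What to change.** Amend the paragraph in SAP 14.2 before unmasking:

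1. Limit the exclusion to AEs that began before treatment and did not worsen on or after the day treatment was initiated. These are listed only.
2. State that an AE that began before treatment and then worsened is a TEAE and is tabulated at its on-treatment maximum severity.
3. State that *prior to treatment* means before the day of first dose, so that both sentences use the same day-based boundary.

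It would also help to say whether worsening is entered as a new AE record or as a severity change on the existing one, so that the programmer can identify these events.

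The cost is a few lines of SAP text and the matching line in the TEAE derivation. It adds no visit or assessment and changes no efficacy analysis. The day-based boundary needs no time-of-onset field. If the eCRF holds only one severity per AE record, the on-treatment maximum cannot be derived from it. In that case the recording convention has to be settled first.
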